8.1.1 Assessment of Adverse Events

The PI ([name]) is primarily responsible for the reporting of adverse events; all members of the research staff are responsible for the assessment of adverse events. All spontaneous reports by participants, observations by research staff, reports to research staff by family or medical care providers, etc., will be investigated. The investigators will assess the relationship of the adverse event as not related, unlikely to be related, possibly related, probably related, or definitely related using standard criteria for clinical trials.

9 DATA AND SAFETY MONITORING PLAN

9.1 Adverse Events and Serious Adverse Events

9.1.1 Definition of Adverse Events (AE)

Adverse event means any untoward medical occurrence associated with the use of an intervention in humans, whether or not considered intervention-related.

9.1.2 Definition of Serious Adverse Events (SAE)

An adverse event (AE) or suspected adverse reaction is considered "serious" if, in the view of either the investigator or sponsor, it results in any of the following outcomes:

- death,
- a life-threatening adverse event,
- inpatient hospitalization or prolongation of existing hospitalization,
- a persistent or significant incapacity or substantial disruption of the ability to conduct normal life functions, or
- a congenital anomaly/birth defect.

Important medical events that may not result in death, be life-threatening, or require hospitalization may be considered serious when, based upon appropriate medical judgment, they may jeopardize the participant and may require medical or surgical intervention to prevent one of the outcomes listed in this definition. Examples of such medical events include allergic bronchospasm requiring intensive treatment in an emergency room or at home, blood dyscrasias or convulsions that do not result in inpatient hospitalization, or the development of drug dependency or drug abuse.

9.1.3 Classification of an Adverse Event

9.1.3.1 Severity of Event

For adverse events (AEs) not included in the protocol defined grading system, the following guidelines will be used to describe severity.

- **Mild** – Events require minimal or no treatment and do not interfere with the participant's daily activities.
- **Moderate** – Events result in a low level of inconvenience or concern with the therapeutic measures. Moderate events may cause some interference with functioning.
- **Severe** – Events interrupt a participant's usual daily activity and may require systemic drug therapy or other treatment. Severe events are usually potentially life-threatening or incapacitating. Of note, the term "severe" does not necessarily equate to "serious".

9.1.3.2 Relationship to Study Intervention

All adverse events (AEs) must have their relationship to study intervention assessed by the clinician who examines and evaluates the participant based on temporal relationship and his/her clinical judgment. The degree of certainty about causality will be graded using the categories below. In a clinical trial, the study product must always be suspect.

- **Definitely Related** – There is clear evidence to suggest a causal relationship, and other possible contributing factors can be ruled out. The clinical event, including an abnormal laboratory test result, occurs in a plausible time relationship to study intervention administration and cannot be explained by concurrent disease, other drugs or chemicals, or other interventions.

- **Probably Related** – There is evidence to suggest a causal relationship, and the influence of other factors is unlikely. The clinical event, including an abnormal laboratory test result, occurs within a reasonable time after administration of the study intervention, is unlikely to be attributed to concurrent disease, other drugs or chemicals, or other interventions.
- **Possibly Related** – There is some evidence to suggest a causal relationship (e.g., the event occurred within a reasonable time after administration of the trial intervention). However, other factors may have contributed to the event (e.g., the participant's clinical condition, other concomitant events). Although an AE may rate only as "possibly related" soon after discovery, it can be flagged as requiring more information and later be upgraded to "probably related" or "definitely related", as appropriate.
- **Unlikely to be related** – A clinical event, including an abnormal laboratory test result, whose temporal relationship to study intervention makes a causal relationship improbable (e.g., the event did not occur within a reasonable time after of the study intervention) and in which other drugs or chemicals, interventions, or underlying disease provides plausible explanations (e.g., the participant's clinical condition, other concomitant treatments).
- **Not Related** – The AE is completely independent of study intervention, and/or evidence exists that the event is definitely related to another etiology. There must be an alternative, definitive etiology documented by the clinician.

9.1.3.3 Expectedness

The Principal Investigator will be responsible for determining whether an adverse event (AE) is expected or unexpected by assessing all AEs against cumulative study intervention experience. Expectedness for adverse events and expectedness for the purposes of expedited reporting will be determined based on review of the following reference documents that describe the nature, severity, and frequency of the events.

9.1.4 Time Period and Frequency for Event Assessment and Follow-Up

The occurrence of an adverse event (AE) or serious adverse event (SAE) may come to the attention of study personnel during study visits and interviews of a study participant presenting for medical care, or upon review by a study monitor.

All AEs related, probably related or possibly related to the study intervention including local and systemic reactions not meeting the criteria for SAEs will be captured on the appropriate case report form (CRF). Information to be collected includes event description, time of onset, clinician's assessment of severity, relationship to study intervention (assessed only by those with the training and authority to make a diagnosis), and time of resolution/stabilization of the event. AEs that are deemed related, probably related or possibly related to the study intervention that occur while on study must be documented appropriately. AEs will be followed to adequate resolution.

Any medical condition (including a laboratory abnormality) that is present at the time that the participant is screened will be considered as baseline and not reported as an AE. However, if the study participant's baseline medical condition worsens at any time during the study and the change is deemed related, probably related or possibly related to the study intervention, it will be recorded as an AE.

Changes in the severity of an AE will be documented to allow an assessment of the duration of the event at each level of severity to be performed. AEs characterized as intermittent require documentation of onset and duration of each episode.

The Clinical Coordinator will record all reportable events with start dates occurring any time after informed consent is obtained until the last day of study intervention. At each study visit, the investigator will inquire about the occurrence of AE/SAEs since the last visit. Events will be followed for outcome information until resolution or stabilization.

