9.1.5 Adverse Event Reporting

Add adverse events will be reported to the University of Virginia IRB-HSR according to guidelines. Any unanticipated problem or serious and unexpected adverse events will require re-evaluation of the risk of the study. [name] will be the person to whom all unanticipated problems or serious and unexpected adverse events, whether psychological or medical, are initially reported. [name] is a licensed clinical psychologist who can evaluate whether the events are SAEs or AEs. [name] will be responsible for ensuring that all unanticipated problems or serious and unexpected adverse events are reported within 48 hours to the IRB and NCATS. Adverse events will be monitored carefully and any necessary steps will be taken to maintain participant safety. Any change to the procedures will be forwarded to the IRB for approval. The NCATS Project Officer will receive an annual report summarizing all adverse events.

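### Section 9.1.4 gives a CRF rule for adverse events judged at least possibly related but none for the rest, so the promised summary of all adverse events cannot be completed from the CRF alone

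*Combined protocol and SAP*

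**What the plan says.** Four parts of the combined protocol and SAP bear on which adverse events are recorded.

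- **Definition (9.1.1).** "Adverse event means any untoward medical occurrence associated with the use of an intervention in humans, whether or not considered intervention-related". Relatedness plays no part in whether something is an adverse event.
- **Causality (9.1.3.2).** Every adverse event must be rated on five levels: definitely, probably and possibly related, unlikely to be related, and not related. Section 8.1.1 lists the same five.
- **Capture (9.1.4).** The events to be entered on the CRF are "All AEs related, probably related or possibly related to the study intervention", and the duty to document events that occur on study is limited in the same way. A condition present at screening counts as baseline and is not reported as an adverse event. If it worsens and "the change is deemed related, probably related or possibly related to the study intervention, it will be recorded as an AE".
- **Reporting (9.1.5).** "The NCATS Project Officer will receive an annual report summarizing all adverse events". The data and safety monitoring plan in appendix 13.1 repeats this commitment.

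Section 9.1.4 also has the clinical coordinator record all reportable events from consent to the end of the intervention, but the protocol does not define reportable.

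**The concern.** The capture rule is narrower than both the definition that precedes it and the report that follows it. A CRF completed as 9.1.4 describes would hold no entry for an event rated unlikely or not related. The annual summary of all adverse events could then not be completed from the CRF, and the five-level causality rating could not be tabulated.

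This has some practical weight here. Section 2.3.1 names tiredness from sleep restriction as a risk of the intervention. Section 2.2 says that poor sleep already contributes to caregivers' anxiety, depression and physical morbidity. A mood or fatigue event therefore has a ready explanation other than SHUTi, and a rating of unlikely is easy to reach. Section 9.1.3.2 foresees that a rating of possibly related may be raised later as information arrives. An event that never reached the CRF is harder to revisit, and with one arm (4.1) there is no comparison group against which to check event rates.

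**Working it through.** The documents state no figure on this point, and no formula applies. The check sets the sections side by side.

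**Step 1: causality categories against the capture rule.** This assumes that *related* in 9.1.4 means *definitely related* in 9.1.3.2.

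| Category (9.1.3.2) | Must be rated | CRF rule in 9.1.4 | Within the annual report (9.1.5) |
|---|---|---|---|
| Definitely related | yes | yes | yes |
| Probably related | yes | yes | yes |
| Possibly related | yes | yes | yes |
| Unlikely to be related | yes | none stated | yes |
| Not related | yes | none stated | yes |

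Three of five categories have a CRF rule, and 5 − 3 = 2 have none. That counts categories, not events. The documents give no expected event rates, so the share of events affected cannot be calculated.

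**Step 2: is the definition itself contradicted?** For a new event, 9.1.1 says what an adverse event is and 9.1.4 says which ones go on the form. The second is narrower, but the two can coexist. For a worsened baseline condition they cannot. Section 9.1.4 starts from the position that the condition is not an adverse event and lifts that where the worsening is judged at least possibly related. Relatedness then decides whether it is an adverse event at all, which 9.1.1 rules out. This is the most direct contradiction.

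**Step 3: what other routes catch events rated unlikely or not related?**

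| Type of event | Route that does not depend on relatedness |
|---|---|
| Serious and unexpected | 48-hour report to the IRB and the funder (9.1.5, appendix 13.1) |
| Serious but expected | no explicit capture rule found |
| Non-serious | no explicit capture rule found |

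The unanticipated-problem route does not fill the gap, because appendix 13.1 requires such a problem to be at least possibly related. The reporting table at 11.5.3 names serious, unexpected and related events with a 7-day limit. It does not cancel the 48-hour route, but it adds no route for unrelated events.

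**Step 4: can the annual report be completed?** It covers all five categories, while the CRF has a rule for three. It would have to draw on some other record, and the protocol does not say which.

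**The case against.** The strongest reply is that 9.1.4 nowhere says other events go unrecorded. It lists what goes on the CRF, has investigators ask about adverse events at each visit, and has reportable events recorded. A reader might infer an express rule that only related events are kept. The text does not state that. The gap is inferred from a relatedness limit that appears three times in one section, together with the absence of any CRF rule for the other two categories. The inference is sound, but it is an inference.

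A reader might also infer that unrelated events leave no trace. The documents do not support that. A rating of not related requires the clinician to document an alternative cause (9.1.3.2). All spontaneous reports are investigated (8.1.1). Section 9.1.5 opens with what appears to be a misprint for reporting all adverse events to the IRB under its guidelines, and appendix 13.1 marks the box for all adverse events. What is missing is a CRF rule, not every record.

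Two further readings go too far. One is that unblinded judgement biases the safety data. With one arm there is no allocation to mask and no between-arm comparison to distort, so this adds nothing. The other is that the principal investigator oversees safety alone. Section 11.3 gives that role the responsibility and there is no independent board, but 11.4 has the project investigators discuss serious and unexpected events at twice-monthly meetings.

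After these concessions the inconsistency remains: following 9.1.4 as written does not yield what 9.1.5 promises.

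**Conclusion.** The point holds as a minor inconsistency with a real consequence. Sections 9.1.1, 9.1.3.2, 9.1.4 and 9.1.5 and the monitoring plan in appendix 13.1 do not agree on which adverse events are recorded and where. The conflict is sharpest for worsening of a baseline condition.

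The exposure is mainly non-serious events, and serious but expected events, rated unlikely or not related. Safety is not among the objectives or endpoints in section 3, and section 10.3 plans no analysis of adverse events. The primary endpoint, the sample size and the secondary analyses are therefore untouched. The conclusion rests on two readings: that the limit in 9.1.4 is meant as a limit, and that the undefined term *reportable* does not bring the other events onto the CRF. If the sponsor intends it to do so, the protocol should say so.

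**What to change.** Reconcile 9.1.1, 9.1.3.2, 9.1.4, 9.1.5 and the monitoring plan in appendix 13.1:

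- In 9.1.4, enter every reported adverse event as defined in 9.1.1 on the CRF, including any worsening of a baseline condition, with its five-level causality rating as a field. Relationship to the intervention is already among the items that 9.1.4 collects.
- Apply relatedness when deciding what is reported, to whom and how fast, not when deciding what is recorded. Define *reportable* at the same time, and check that the table at 11.5.3 agrees with the 48-hour route.
- In the annual report, summarise all events and related events separately.

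The cost is protocol wording and a few more form entries in a study with a minimum of 100 and a maximum of about 130 participants (10.2). Naming in 9.1.5 which other records feed the annual report would address the reporting conflict, but it would leave the baseline-worsening contradiction and the gap in the CRF.

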8 STUDY ASSESSMENTS AND PROCEDURES

8.1 Study Materials and Methods

Participating caregivers will be instructed on how to complete the pre-assessment battery of online questionnaires using either computer or mobile device as the participant prefers. Estimated completion times are 30 minutes for questionnaires. Upon completing questionnaires, participants will complete 10 daily sleep diaries within 14 days. Participants will be compensated \$40 upon pre-assessment completion.

After participants complete pre-assessment, they will receive access to SHUTi. Participants will be emailed a unique username and password in order to log on and securely access SHUTi for 9 weeks. The intervention can be accessed via an Internet enabled device, including a computer, tablet, or smartphone. At the start of week ten, regardless of intervention progress, participants will be instructed to complete their online post assessment.

Non-users' (i.e., those who completed 0 SHUTi Cores) post-assessment will include an open-ended survey regarding barriers to SHUTi adoption, the extent to which barriers were related to caregiving, and what modifications may have increased their motivation to try SHUTi. Users' (i.e., those who completed 1 or more SHUTi Cores) post-assessment will include an open-ended survey assessing SHUTi usage barriers and motivations, the extent to which these were related to caregiving, and how tailoring may improve usage by increasing salience to caregivers. SHUTi users will also complete 10 daily sleep diaries in 14 days as part of post-assessment. Participants will be compensated \$40 upon post-assessment completion.

Caregivers who agree to be contacted for follow-up will be returned a concise report of results from the analyses as part of synthesized member checking procedures, where caregivers will be asked to review the report and comment on how results compare/contrast with their experiences and needs.

Sources of research materials:

The sources of research material will include:

- (1) self-report questionnaires completed over the Internet (including caregiving-related user- and environment characteristics; as well as demographics, sleep, self-efficacy and other health/psychosocial constructs);
- (2) telephone interview to inquire about sleep problems, insomnia treatment history, and computer/Internet usage;

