11.3 Safety Oversight

The study PI will be responsible for the safety oversight for this trial. AEs will be monitored throughout the study.

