13 APPENDICES

13.1 Schedule of Activities (SoA)

Procedures	Eligibility / Enrollment Day 0	Pre-Assessment Day 0 + 14 Days	SHUTi intervention period Completion of sleep diaries	Post-assessment 9 weeks post-SHUTi initiation +14 days
Eligibility screening	X			
Informed consent	X			
Pre-assessment (online questionnaires)		X		
Baseline sleep diaries		X		
Access to SHUTi (study intervention)			X	
Post-assessment (online questionnaires)				X
Follow-up sleep diaries				X

Data and Safety Monitoring Plan: IRB-HSR serves as sIRB of Record

13.1.1.1.1.1

DEFINITIONS:**1.3 What is the definition of an unanticipated problem?**

Do not change this answer

An unanticipated problem is any event, experience that meets ALL 3 criteria below:

- Is unexpected in terms of nature, severity or frequency given the research procedures that are described in the protocol-related documents AND in the characteristics of the subject population being studied
- Related or possibly related to participation in research. This means that there is a reasonable possibility that the incident may have been caused by the procedures involved in the research study.
- The incident suggests that the research placed the subject or others at greater risk of harm than was previously known or recognized OR results in actual harm to the subject or others

Additional Information: see the IRB-HSR website at

Protocol Deviations, Non-compliance and Protocol Exceptions

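### No adverse event inquiry is scheduled once SHUTi access begins, and the protocol gives inconsistent end points for the onset window

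*Combined protocol and SAP*

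**What the plan says.** **How events are found.** Section 9.1.4 states: "At each study visit, the investigator will inquire about the occurrence of AE/SAEs since the last visit". It also mentions events noticed when a participant presents for medical care or on review by a study monitor. Section 8.1.1 lists further sources to be investigated: "All spontaneous reports by participants, observations by research staff", and reports from family or medical providers.

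**What must be recorded.** For events judged at least possibly related, Section 9.1.4 requires a case report form with a description, onset time, severity, relationship to the intervention, and time of resolution or stabilisation.

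**For how long.** Section 9.1.4 has the coordinator record reportable events "with start dates occurring any time after informed consent is obtained until the last day of study intervention". The same section says that related events "that occur while on study must be documented appropriately". Section 11.3 says "AEs will be monitored throughout the study".

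**What contact is planned.** Under Section 8.1, participants complete an online pre-assessment, receive login details by email, and can "securely access SHUTi for 9 weeks". They are told at the start of week ten to complete an online post-assessment. The Schedule of Activities gives that assessment a 14-day window.

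**The concern.** A rule tied to visits works only if there are visits. In this trial the live contacts that the protocol describes serve screening and consent, so they precede exposure to SHUTi and cannot detect harm from it.

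The trial has a named, treatment-specific risk. Section 2.3.1 says that restricting sleep may at first leave participants more tired, and the risk plan in the appendix has them told not to drive or use heavy machinery when tired. Section 9.1.5 commits the study to reporting adverse events to the IRB and to an annual summary of all of them for NCATS. If nobody is scheduled to ask, a low count in that summary cannot be told apart from a count that is low because the question was not put. Section 7.2 also makes adverse events a ground for discontinuing study treatment, which presupposes that the site hears of them.

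**Working it through.** The plan states no figure to reproduce, so the check compares passages and adds up the timeline.

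**Step 1. Is there a contact at which the visit rule can operate?**

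| Contact in the documents | When | Adverse event inquiry? |
|---|---|---|
| Consent by phone or in clinic (11.1) | Before treatment | Precedes exposure |
| Telephone interview (8.1) | No date given; content is sleep problems, treatment history and computer use | None listed |
| Pre-assessment (8.1, 13.1) | Online, before access | None listed |
| SHUTi access with automated email reminders (2.2.1, 8.1) | Nine weeks, self-guided | None listed |
| Post-assessment (8.1, 13.1) | Online, from week ten | None listed |
| Contact after missed assessments (7.2) | Unscheduled | Purpose is encouragement and willingness to continue |
| Member checking (8.1, 10.3.2) | After analysis, for those who agree | Comments on results only |

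Scheduled adverse event inquiries after access begins: 0.

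**Step 2. Does the survey battery fill the gap?** The survey table in Section 8.1 repeats physical health (PROMIS), distress (PHQ-4) and the Insomnia Severity Index at post-assessment for everyone, and sleep diaries for users. These are scores. None asks whether an event occurred, when it began, or whether it may be related, which is what Section 9.1.4 requires on the form.

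**Step 3. What does the onset window cover?** Take the last day of intervention to be the end of the nine-week access period, and count from the first day of access.

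- Access: 9 × 7 = 63 days, so days 1 to 63.
- Post-assessment: 14 days, so about days 64 to 77.
- The onset limit "until the last day of study intervention" closes at about day 63. Events starting on days 64 to 77 fall outside it.
- The statements about events on study and monitoring throughout the study would include those days.

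From Day 0, with both 14-day windows used in full, 14 + 63 + 14 = 91 days. The onset window covers 14 + 63 = 77 of them, or 77/91 = 85%. If the 12-week participant duration in the synopsis governs instead, the total is 84 days and 84 − 77 = 7 days lie outside. The uncovered period is therefore 7 to 14 days, depending on which duration applies.

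**The case against.** The strongest reply is that the study has other ways of learning about events. Section 8.1.1 names staff observation and family or provider reports. Section 9.1.4 adds monitor review, and Section 7.2 has the site contact people who miss assessments. The appendix tells participants to contact staff with concerns, tracks all staff interactions, and provides for referral when urgent need becomes evident. Repeated health scores and sleep diaries may show worsening without anyone volunteering it. A reader might infer that events would be captured only if participants volunteer them; these provisions show that this is too strong. What stands is that every such route is passive, incidental or unscheduled, and that staff have little to observe in a remote programme without human therapy support.

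A reader might also infer that recording stops before the post-assessment. The text does not say so. The limit applies to start dates, so tiredness that began in week five and was mentioned at post-assessment could still be recorded. The window problem is one of inconsistency.

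It is also fair to say that safety is neither an endpoint nor a hypothesis here, that the primary and secondary conclusions are unaffected, and that the appendix already includes measures against tiredness. These points limit the consequence. They do not make the visit rule workable, and they do not remove the commitment to summarise adverse events.

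**Conclusion.** The concern holds in this form: after SHUTi access begins, no scheduled adverse event inquiry is specified, the one active rule has no visit to attach to, and the statements on the collection window disagree over a period of up to 14 days. The adverse event summary is likely to be incomplete as a result.

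The size of the shortfall cannot be estimated. The documents give neither an expected event rate nor a reporting rate, and putting assumed values on either would only return the assumption. It would also be wrong to infer that the sponsor intends to claim an absence of harm, since nothing in the documents says so.

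The conclusion assumes that the Schedule of Activities and the survey table list all planned contacts and measures, and that the last day of intervention means the end of the nine-week access period. The change should be made, because it is what makes the stated safety plan executable. It does not bear on the validity of the primary analysis.

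**What to change.** 1. Add one or two adverse event items to the existing online post-assessment, for users and non-users alike. They should ask about any new or worsened health problem, marked daytime sleepiness, accident or hospitalisation since access began, with the date of onset.
2. Add an adverse event row to the Schedule of Activities.
3. In Section 9.1.4, replace the visit-based inquiry with this one.
4. Reconcile Sections 9.1.4, 11.3 and 13.1 to a single collection window that runs through completion of post-assessment.

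The cost is a slightly longer questionnaire and a little staff time to follow up positive answers. One question at the end relies on recall over about nine weeks and gives no information while treatment is under way, and the report should say so. No new visit is needed and clinical management is unchanged.
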